8.6.1.1. Modified US FDA-Defined Snapshot Alogrithm

The US FDA-defined snapshot algorithm, developed for HIV-1 clinical trials, has been modified for use in HBV {U. S. Department of Health and Human Services 2015} using on-treatment HBV DNA values of < 20 IU/mL and ≥ 20 IU/mL.

The analysis window at Week 48 is defined as from Study Day 294 to Study Day 377, inclusive. All HBV DNA data collected on-treatment will be used in the snapshot algorithm. Virologic outcome will be defined as the following categories:

- **HBV DNA < 20 IU/mL:** this includes subjects who have the last available on-treatment HBV DNA < 20 IU/mL in the Week 48 analysis window
- HBV DNA \geq 20 IU/mL: this includes subjects who
 - 1) Have the last available on-treatment HBV DNA ≥ 20 IU/mL in the Week 48 analysis window, or
 - 2) Do not have on-treatment HBV DNA data available in the Week 48 analysis window and
 - a) Discontinue study drug prior to or in the Week 48 analysis window due to lack of efficacy, or
 - b) Discontinue study drug prior to or in the Week 48 analysis window due to reason other than lack of efficacy and have the last available on-treatment HBV DNA ≥ 20 IU/mL

- No Virologic Data in the Week 48 Analysis Window: this includes subjects who do not have on-treatment HBV DNA data available in the Week 48 analysis window for any of the following reasons:
 - 1) Discontinuation of study drug prior to or within the Week 48 analysis window due to reasons other than lack of efficacy and the last available on-treatment HBV DNA value is < 20 copies/mL, or
 - 2) Missing data within the window but who are on study drug treatment

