6.3.1.6. Week 48 (visit window is -14 days)

- Complete physical examination with vital signs (blood pressure, pulse, respiration rate and temperature) and body weight
- ECG (subjects must rest quietly in the supine position for a minimum of 5 minutes prior to the recording)
- DXA scan of hip and spine (within -14 days of the expected visit date)
- Review concomitant medications
- Review adverse events
- Perform study drug accountability
- Fasting blood sample for bone biomarkers and metabolic assessment (glucose and lipid panel [total cholesterol, HDL, direct LDL, and triglycerides]) no food or drinks, except water, at least 8 hours prior to blood collection
- Fasting urine sample for renal biomarkers
- Blood sample for serum chemistry and liver function tests, hematology, PT/INR, plasma HBV DNA, serum HBsAg (quantitative), HBV serology (qualitative HBsAg and HBeAg), virology (resistance surveillance), PPD
- Estimated creatinine clearance (using the Cockcroft-Gault method)
- Child-Pugh Score (Assessment requires: total bilirubin, albumin, PT/INR, Ascites assessment, and Hepatic encephalopathy assessment)
- Blood sample for Fibrotest[®]
- PPD
- Urine sample for urinalysis, pregnancy test (for females of child-bearing potential; in case of a positive urine test, a serum pregnancy test will be done), PPD
- Health Related Quality of Life (HRQoL) Surveys (CLDQ, SF-36, WPAI)
- Retrieve blinded study drug and dispense open label study drug

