6.8. Resistance Surveillance and Virologic Rebound Management

Sequence analysis of the HBV polymerase/reverse transcriptase (pol/RT) for potential resistance mutations may be attempted for any subject with HBV DNA \geq 69 IU/mL at Baseline and for subjects who experience viremia (HBV DNA \geq 69 IU/mL) at Weeks 48 and 96/ED. Phenotypic analysis will be performed for subjects that are subjected to sequence analysis.

As it may not be known at the time of the visit whether a patient is viremic or if it will be their last study visit, a separate serum sample for potential resistance surveillance will be collected at each study visit.

In the event of unconfirmed virologic rebound (HBV DNA \geq 20 IU/mL), subjects will be asked to return to the clinic for a scheduled or unscheduled blood draw. For virologic rebound occurring within the first 12 weeks of the study, the next scheduled visit will used for follow up. For virologic rebound occurring after Week 12, the subject will return for an unscheduled visit within 2-3 weeks after the date of the original test that resulted with HBV DNA virologic rebound for confirmation of virologic rebound. At this follow up visit, a serum blood sample for resistance testing will be obtained. For unscheduled visits, the subject will be required to bring their supply of study drug with them and be assessed for adherence by pill count, and if necessary, the subject will be re-counseled on adherence to study medication.

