3.6.2. Analysis Windows

Subject visits might not occur on protocol specified days. Therefore, for the purpose of analysis, observations will be assigned to analysis windows.

The following windows (Table 3-1 to Table 3-6) apply only to baseline and postbaseline on-treatment assessments collected during the double-blind phase and open-label phase. For summaries and analyses, assessments will first be categorized into baseline and postbaseline on-treatment assessments occurring during the double-blind or open-label phase before applying analysis windows.

Baseline value for the double-blind phase is defined as the last nonmissing value obtained on or prior to Study Day 1. For DXA BMD, it is defined as the last value on or prior to Study Day 14.

For subjects who completed blinded study drug and entered the open-label phase, laboratory assessments that occurred during the period from Study Day 2 up to and including the minimum of the Last Dose Date of Blinded Study Drug + 3 days and Open-label Study Day 1, will be considered as postbaseline on-treatment assessments during the double-blind phase. If a subject prematurely discontinued blinded study drug or did not enter open-label phase after completion of blinded study drug, then postbaseline on-treatment assessments during the double-blind phase will be defined as assessments that occurred during the period from Study Day 2 up to and including the Last Dose Date of Blinded Study Drug + 3 days. DXA assessments that occurred during the period from Study Day 15 up to and including the Last Dose Date of Blinded Study Drug + 14 days will be considered as postbaseline on-treatment assessments during the double-blind phase.

Baseline value for the open-label phase is defined as the last nonmissing value obtained on or prior to Open-Label Study Day 1. For DXA BMD, it is defined as the last value on or prior to Open-Label Study Day 14.

For subjects who entered the open-label phase, postbaseline on-treatment assessments during the open-label phase will be defined as assessments that occurred during the period from Open-label Study Day 2 up to the Last Dose Date + 3 days. DXA assessments that occurred during the period from Open-label Study Day 15 up to the Last Dose Date + 14 days will be considered as postbaseline on-treatment assessments during the open-label phase.

Baseline value for the TFFU phase is defined as the last nonmissing value obtained on or prior to the Last Dose Date + 3 days.

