For baseline of the double-blind, open-label, and TFFU phases, the last available record on or prior to the first dose of blinded study drug, open-label study drug, and last dose date + 4 days will be selected, respectively. For DXA BMD baseline, the last value on or prior to Study Day 14 and Open-Label Study Day 14 will be selected for the double-bind and open-label phases, respectively. If there are multiple records with the same time or no time recorded on the same day for numeric observations, the average will be computed for that day, except for HBV DNA and quantitative HBsAg the geometric mean will be taken instead. If there are multiple records with the same time or no time recorded on the same day for categorical observations, the most conservative value will be taken, eg, negative will be selected over positive for HBeAg and HBsAg, and positive will be selected over negative for HBeAb and HBsAb.

The following specified rules will be used for postbaseline visits:

- **ALT:** The largest value will be included in the analysis when 2 or more ALT values occur within the same visit window.
- **BMD:** The latest record in the window will be selected
- **HBV DNA (IU/mL):** The record on the latest day in the window will be selected. If there is more than 1 record on the selected day, the geometric mean will be taken.
- Quantitative HBsAg (IU/mL): The record closest to the nominal day for that visit will be selected. If there are 2 records equidistant from the nominal day, the latest will be selected. If there is more than 1 record on the selected day, the geometric mean will be taken.
- **Serology:** For HBeAg, HBeAb, HBsAg, and HBsAb, the record closest to the nominal day for that visit will be selected. If there are 2 records equidistant from the nominal day, the latest will be selected. If there is more than 1 record on the selected day, the most conservative value will be taken, ie, positive will be selected over negative for HBeAg and HBsAg, and negative will be selected over positive for HBeAb and HBsAb.

For all other laboratory parameters:

• If multiple valid non-missing **numeric** observations exist in a window, then records will be chosen as follows:

The record closest to the nominal day for that visit will be selected. If there are 2 records equidistant from the nominal day, the latest will be selected. If there is more than 1 record on the selected day, the average will be taken.

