6. EFFICACY ANALYSES

For the final analysis, efficacy data will be summarized for (1) subjects in the FAS from baseline up to Week 96 and statistical comparisons will be performed, (2) subjects in the Open-Label FAS from open-label baseline up to Week 96 and no statistical comparisons will be performed, and (3) subjects in the TFFU FAS from TFFU baseline to the end of the study and no statistical comparisons will be performed. All efficacy data, including data collected during the 24-week TFFU period, will be listed.

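### Protocol 8.6.1.1 does not limit the Week 48 HBV DNA value to blinded drug, so as written a rebound retest taken on open-label TAF could replace a Week 48 failure.

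*Protocol*

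**What the plan says.** Protocol 8.6.1.1 sets the window ("The analysis window at Week 48 is defined as from Study Day 294 to Study Day 377, inclusive") and the data admitted to it: "All HBV DNA data collected on-treatment will be used in the snapshot algorithm". The last available on-treatment value in the window decides between success and failure. The section does not define treatment as blinded drug, and it does not end the data at the switch.

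Protocol 6.3.1.6 gives the Week 48 visit a window of minus 14 days only and lists among its procedures: "Retrieve blinded study drug and dispense open label study drug". Protocol 6.8 covers HBV DNA of 20 IU/mL or more after Week 12: "the subject will return for an unscheduled visit within 2-3 weeks after the date of the original test". It makes no exception for a rebound found at Week 48.

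The SAP is more careful about phases. Under SAP 3.6.2, "assessments will first be categorized into baseline and postbaseline on-treatment assessments occurring during the double-blind or open-label phase before applying analysis windows". For subjects who enter the extension, double-blind laboratory data end at "the minimum of the Last Dose Date of Blinded Study Drug + 3 days and Open-label Study Day 1". However, SAP 6.1.1 does not re-analyse the primary endpoint and refers to a separate Week 48 SAP. The SAP's own FAS efficacy summaries cover "subjects in the FAS from baseline up to Week 96 and statistical comparisons will be performed". Table 3-1 sets HBV DNA windows in Study Days running through both phases (Week 48 is Day 295-378), and SAP 3.6.3 says of HBV DNA: "The record on the latest day in the window will be selected".

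**The concern.** The Protocol schedules the very sample that can overwrite its primary outcome. A subject with a value of 20 IU/mL or more at the Week 48 visit starts open-label TAF and returns for a retest while the Week 48 window is still open. If the retest is below 20 IU/mL, it is the last on-treatment value and the subject becomes a success.

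Two things follow. First, the overwriting is selective. The next scheduled visit is Week 60, outside the window, so post-switch values come mainly from subjects who have just failed. Suppressed subjects supply one only occasionally, for example from reflex testing after a confirmed ALT elevation or at an early discontinuation visit. Second, in the TDF arm the replacing value is measured on TAF, so it no longer describes the randomised comparison.

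The direction of the bias is not fixed. Clearing failures in both arms shrinks the difference and favours non-inferiority. Clearing mainly TDF failures widens it and works against non-inferiority.

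**Working it through.** **1. The plan's own power figure.** Inputs from Protocol 8.9: 230 per arm, 2.4% failures in both arms, margin 4%, one-sided 0.025.

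- SE = √(2 × 0.024 × 0.976 / 230) = 0.01427
- Power = Φ(0.04 / 0.01427 − 1.96) = Φ(0.843) = 80.0%

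The stated 80% is reproduced. Expected failures are 230 × 0.024 = 5.5 per arm.

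**2. Retest dates.** Week 48 is nominal Day 336 (SAP Table 3-1).

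- Visit: 336 − 14 = Day 322, to Day 336
- Earliest retest: 322 + 14 = Day 336
- Latest retest: 336 + 21 = Day 357

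Day 336-357 lies wholly inside both Day 294-377 (Protocol) and Day 295-378 (SAP). A retest after a rebound at Week 36 (visit Day 249-255) falls on Day 263-276, before either window, so the overlap arises at Week 48. Week 60 is Day 420, outside both.

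**3. Effect on the test.** Let e be the share of failures that can be overwritten, and rT and rD the shares of those that clear in the TAF and TDF arms. The documents give none of these; they are assumptions. The observed failure rates become true TAF rate × (1 − e·rT) and true TDF rate × (1 − e·rD). The probability that the upper 95% limit is below 4% is summed over the exact binomial distributions, using an unstratified Wald interval with 230 per arm. The planned interval is stratified Mantel-Haenszel, so these are illustrations.

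True rates at the margin (TAF 2.4% + 4% = 6.4%, TDF 2.4%):

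| rT / rD | Chance of declaring non-inferiority, e = 1 | e = 0.5 |
|---|---|---|
| 0 / 0 | 3.2% | 3.2% |
| 20% / 20% | 8.4% | 5.2% |
| 50% / 50% | 34.5% | 10.7% |
| 0 / 30% | 1.4% | 2.1% |
| 0 / 50% | 0.7% | 1.6% |

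For example, with e = 1 and 50% clearing in both arms, the observed rates are 6.4% × 0.5 = 3.2% and 2.4% × 0.5 = 1.2%. The e = 1 column is an upper range. Failures through discontinuation, and failures in subjects who do not enter the extension, cannot be overwritten in this way; e = 0.5 allows for them.

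With both true rates at 2.4% and e = 1, exact power is 79.0% with no overwriting, 95.7% if 50% clear in both arms, and 61.7% if 50% clear in the TDF arm only.

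**4. Single subjects.** Upper limit = difference + 1.96 × SE, 230 per arm:

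| TAF v TDF failures | Difference | SE | Upper limit | Non-inferiority |
|---|---|---|---|---|
| 8 v 5 | 1.30% | 1.544% | 4.33% | not met |
| 7 v 5 | 0.87% | 1.486% | 3.78% | met |
| 7 v 4 | 1.30% | 1.423% | 4.09% | not met |

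Overwriting one TAF failure moves 8 v 5 to 7 v 5 and reverses a failed test. Overwriting one TDF failure moves 7 v 5 to 7 v 4 and reverses a successful one.

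**The case against.** The strongest reply is that the SAP already has the rule. SAP 3.6.2 sorts assessments by phase before windowing, HBV DNA heads the list in Table 3-1, and sorting by phase has little purpose unless it keeps post-switch values out of double-blind visits. That is a fair reading, and under it the retest is excluded. It does not settle the matter. This SAP covers the final analysis and leaves the primary endpoint to another document. Its Week 48 windows run in Study Days through both phases, with the latest-day record chosen. Nor does the Protocol text carry the cut-off.

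A second reply is that a TAF-arm retest is still on the randomised drug, so the switch itself contaminates only the TDF arm, where overwriting makes a false claim less likely. That is correct as to the change of drug. In the TAF arm the problem is selective retesting under a last-value rule, and the same missing cut-off lets it in.

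A third is that single subjects matter only near the boundary. This also stands. At counts close to expectation, such as 5 v 5 (2.67%), 6 v 5 (3.23%) or 6 v 4 (3.53%), the test is met with room to spare. With both true rates at 2.4%, removing one TAF failure rescues a failed test in 8.7% of trials, and removing one TDF failure reverses a success in 5.9%.

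Finally, nothing shows that a post-switch value entered the primary result. SAP 2.2 reports the Week 48 analysis as already conducted, so new Protocol wording cannot govern it after the fact.

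**Conclusion.** The concern holds as a gap in the Protocol text: followed literally, the Week 48 rule lets a retest on open-label TAF replace a Week 48 failure. It is not evidence that the analysis was run that way, because the Week 48 SAP is not available and may have applied the limit.

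The size depends on how many failures could be overwritten and how many would clear, neither of which the documents give. Over the ranges shown, the false non-inferiority rate at the margin runs from 0.7% to 34.5% against 3.2% with no overwriting, and from 1.6% to 10.7% if only half of failures can be overwritten. The point should be fixed. Confidence is medium, since the effect on the reported result turns on an unseen document.

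**What to change.** In Protocol 8.6.1.1, and for every Week 48 HBV DNA endpoint in the SAP, admit only samples taken on or before the earlier of last blinded dose + 3 days and Open-label Study Day 1. This is the sponsor's own SAP 3.6.2 limit. Take the last such value, and report post-switch retests separately.

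For the completed primary analysis, confirm that the Week 48 SAP and its programs applied this limit. If they did not, report the primary result with and without post-switch values.

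Two clerical corrections can go in at the same time: state one Week 48 window (Day 294-377 or Day 295-378), and in Protocol 8.6.1.1 change the unit in the no-virologic-data category from copies/mL to IU/mL.

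The cost is one sentence in each document, one date condition in the programming and a check of the Week 48 SAP. The observed failure rate may be slightly higher.

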8.6.2. Analyses of Secondary Endpoints

Continuous secondary endpoints will be summarized using conventional descriptive statistics (n, mean, standard deviation, median, Q1, Q3, minimum, and maximum) by treatment group and overall. A Wilcoxon rank sum test may be used to compare the treatment groups, in an exploratory manner.

Categorical secondary endpoints will be summarized by number and percentage of subjects that meet the endpoint. A two-sided Mantel-Haenszel test, controlling for the randomization strata, may be used to compare the treatment groups, in an exploratory manner. Missing data will be handled by the missing = failure approach except for the endpoints of HBV DNA \geq 20 IU/mL and HBV DNA \leq 20 IU/mL.

8.7. Safety Analysis

All safety data collected on or after the date that IMP was first dispensed up to the date of last dose of IMP will be summarized by treatment group (according to the IMP received). Data for the pretreatment and treatment-free follow-up periods will be included in data listings.

8.7.1. Key Secondary Safety Analyses

The percent change from baseline in hip and spine BMD at Week 48 will be analyzed using an ANOVA model. The model will include treatment group as fixed effect. The detailswill be provided in the Statistical Analysis Plan (SAP).

The change from baseline in in eGFR $_{CG}$ at Week 48 will be analyzed using a 2-sided Wilcoxon rank sum test to compare the 2 treatment groups. The details will be provided in the SAP.

8.7.2. Extent of Exposure

A subject's extent of exposure to IMP data will be generated from the IMP administration data. Exposure data will be summarized by treatment group.

8.7.3. Adverse Events

Clinical and laboratory adverse events will be coded using the Medical Dictionary for Regulatory Activities (MedDRA). System Organ Class (SOC), High-Level Group Term (HLGT), High-Level Term (HLT), Preferred Term (PT), and Lower-Level Term (LLT) will be attached to the clinical database.

Events will be summarized on the basis of the date of onset for the event. A treatment-emergent adverse event will be defined as any adverse event that begins on or after the date of first dose of IMP up to the date of last dose of IMP. Continuing adverse events diagnosed prior to the start of treatment and worsening in severity grade, or non-serious adverse events at baseline which become serious, or adverse events resulting in treatment discontinuation after the start of treatment will also be considered treatment-emergent. Summaries (number and percentage of subjects) of treatment-emergent adverse events (by SOC and PT) will be provided by treatment group:

- Treatment-emergent adverse events
- Treatment-emergent study drug-related adverse events
- Grade 3 or 4 treatment-emergent adverse event
- Grade 3 or 4 treatment-emergent study drug-related adverse event
- Grade 2, 3, or 4 treatment-emergent adverse event
- Grade 2, 3, or 4 treatment-emergent study drug-related adverse event
- AE that caused permanent discontinuation from study drug
- AE that caused change in dose or temporary interruption of study drug
- Treatment-emergent serious adverse event
- Treatment-emergent study drug-related serious adverse event

8.7.4. Laboratory Evaluations

Selected laboratory data (using conventional units) will be summarized using only observed data. Data and change from baseline at all scheduled time points will be summarized.

Graded laboratory abnormalities will be defined using the grading scheme in Appendix 4.

Incidence of treatment-emergent laboratory abnormalities, defined as values that increase at least one toxicity grade from baseline at any time post baseline up to and including the date of last dose of treatment will be summarized by treatment group. If baseline data are missing, then any graded abnormality (i.e., at least a Grade 1) will be considered treatment emergent.

Laboratory abnormalities that occur before the first dose of IMP or after the subject has been discontinued from treatment will be included in a data listing.

8.8. Biomarker Analysis

Selected bone biomarkers, including C-type collagen sequence (CTX) and procollagen type 1 N-terminal propeptide (P1NP), and selected renal biomarkers, including urine retinol binding protein, and urine beta-2-microglobulin, will be summarized by treatment group and visit using descriptive statistics. The difference in change from baseline in these biomarkers between two treatment arms will be tested using Wilcoxon rank sum test.

8.9. Sample Size

With respect to the primary efficacy endpoint of proportion of suppressed subjects with HBV DNA \geq 20 IU/mL (current assay LLOQ), as determined by the modified US FDA-defined snapshot algorithm, at Week 48, when the sample sizes are 230 (TAF 25 mg arm) and 230 (TDF 300 mg arm), a two-group, large-sample normal approximation test of proportions with a one-sided 0.025 significance level will have 80% power to establish non-inferiority of TAF to TDF. It is assumed that both treatment arms will have subjects who have HBV DNA \geq 20 IU/mL (as defined by the modified US FDA-defined snapshot algorithm) at a rate of 2.4% at Week 48 (based on the rates of suppressed subjects having HBV DNA \geq 29 IU/mL [the LLOQ of assay during those studies] after 48 weeks of treatment from the combined data of studies GS-US-174-0102 and GS-US-174-0103 with the ratio of HBeAg- to HBeAg+ subjects assumed to be 2:1), with a non-inferiority margin of 4%.

The proposed sample size (n = 230 for the TAF 25 mg arm, n = 230 for the TDF 300 mg arm) also provides > 99% power to detect a 1.81% difference in the percentage change from baseline in hip BMD at Week 48 (assuming a 1.47% [SD 2.71%] change from baseline in TAF 25 mg arm and -0.34% [SD 2.83%] change from baseline in the TDF 300 mg arm, with a two-sided $\alpha = 0.05$); a > 99% power to detect a 2.00% difference in the percentage change from baseline in spine BMD at Week 48 (assuming a 1.56% [SD 3.84%] change from baseline in the TAF 25 mg arm and -0.44% [SD 4.14%] change in the TDF 300 mg arm, with a two-sided $\alpha = 0.05$); a 97% power to detect a 4.9 mL/min difference in the change from baseline in eGFR_{CG} at Week 48 (assuming a 1.3 mL/min [SD 13.2] change from baseline in the TAF 25 mg arm and -3.6 mL/min [SD 13.0] change from baseline in the TDF 300 mg arm, with a two-sided $\alpha = 0.05$). These assumptions were derived from an HIV switch study (GS-US-292-0109) due to the unavailability of switch data from TAF HBV studies.

